TITLE: Celecoxib for Thyroid Eye Disease

NCT: 02845336

PI: [name]

DATE: January 21, 2017

Date: January 21, 2017 Principal Investigator: [name] Application Number: IRB00094787

JHM IRB - eForm A – Protocol

- Use the section headings to write the JHM IRB eForm A, inserting the appropriate material in each. If a section is not applicable, leave heading in and insert N/A.
- When submitting JHM IRB eForm A (new or revised), enter the date submitted to the field at the top of JHM IRB eForm A.

1. Abstract

- Thyroid eye disease (TED) is an autoimmume disorder in which autoantibodies against the TSH receptor attack orbital tissues, resulting in characteristic changes in eyelid position, globe position in the orbit, extraocular muscle balance, and optic nerve function. TED is a potentially blinding disease, and current treatments largely consist of nonspecific reduction of inflammation using corticosteroids or radiation therapy. The former treatment has significant morbidity, while the latter is controversial. Rituximab, which depletes CD20+ cells, has been used recently in severe disease but has evoked concern because of its cost and potential morbidity. Regardless of treatment, once TED progresses from its inflammatory phase to a more fibrotic, resolution phase, the orbital changes become fixed and can be modified only by surgery. We intend to use celecoxib (Celebrex), a non-steroidal anti-inflammatory drug approved by the Food and Drug Administration (FDA) for the treatment of pain, osteoarthritis, rheumatoid arthritis, and ankylosing spondylitis, as a treatment for active TED. In vitro data have shown that transformation of orbital fibroblasts into adipocytes is mediated by cyclooxygenase-2 (COX-2) via the PPAR-gamma pathway, and a single case report suggests that COX-2 inhibition can improve TED in the acute phase. Thus, we intend to evaluate the efficacy of COX-2 inhibition in the treatment of active TED and its ability to improve both the acute inflammatory signs and more permanent fibrotic changes of quiescent disease. We will enroll patients with active TED and treat them for 3 months (a characteristic period of disease activity) and compare this to standard treatments for mild TED (observation with only over the counter interventions such as lubrication with artificial tears) to assess efficacy.
- 2. **Objectives** (include all primary and secondary objectives)

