exam to evaluate the potential subject's optic nerve. Photographs (external, eye movements, optic nerve) may be taken as needed. This eye examination is standard of care on any thyroid eye disease patient. Findings from the eye exam will be used to determine a CAS and VISA score. The CAS takes into account 7 manifestations (spontaneous retrobulbar pain, pain with eye movement, eyelid erythema, eyelid edema, conjunctival injection, chemosis, and caruncular swelling) with 1 point assigned for each positive finding. The VISA score ranges from 0-16 based on findings related to inflammation, strabismus, and eyelid changes and proptosis (appearance). Both scales were developed to assess features of active disease that might change with treatment.

- Study subjects will be randomly assigned to observation with no prescription treatment, or treatment with oral celecoxib 100 mg twice daily for 3 months. Patients will have a full clinical exam at baseline, 1 month, 3 months, 6 months, and 12 months, with additional clinical visits more frequently if indicated by disease course/activity. The proposed frequency of clinic visits is within standard of care for newly diagnosed active-phase TED.
- For those subjects randomized to the treatment group, baseline blood testing for blood counts, renal and hepatic function (BUN, Cr, AST, ALT, total bilirubin) will be obtained prior to starting the drug. Testing will be performed by a standard clinical laboratory and billed to insurance. Testing will be repeated at 1mo and 3mo after randomization/initiation of therapy for those receiving celecoxib. Abnormal BUN or creatinine (outside normal range) on lab testing or any previous/current kidney disease will be the criteria for labeling a patient as having impaired renal function. Abnormal liver enzymes (AST, ALT, bilirubin outside normal range) or previous/current liver disease will determine whether a patient is labeled as having impaired hepatic function. Monthly phone interviews also will be conducted by physician study team members to determine if other side effects, such as edema, may be occurring. Subjects will be asked specifically about peripheral swelling, any blood in urine or skin discoloration, or changes in exercise tolerance. Positive responses will trigger an unscheduled visit with the PI or co-investigator MD. Patients will be cautioned not to take additional NSAID medications while on Celecoxib, as this may increase the chance for adverse effects.

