 - There may be other reasons to take subjects out of the study that we do not know at this time.

5. Inclusion/Exclusion Criteria

Eligibility criteria:

- *Recent diagnosis of thyroid eye disease (within the past 6 months)*
- Have ocular symptoms or signs of TED with a CAS score of at least 3
- Ages 18-80 years

Exclusion criteria:

- Pregnancy
- Previous treatment with corticosteroid for TED for >2wks
- Previous treatment with orbital radiation for TED
- Impaired renal function
- Impaired hepatic function
- *Treatment with antihypertensive medications except beta-blockers*
- History of congestive heart failure, cardiac valvular disease, or coronary artery disease
- Allergy to NSAID or previous adverse reaction (ie. GI bleeding)
- Vision loss due to compressive optic neuropathy

Target 40 participants will be enrolled in this study.

6. Drugs/ Substances/ Devices

Celecoxib (Celebrex) is a non-steroidal anti-inflammatory drug approved by the Food and Drug Administration (FDA) for the treatment of pain, osteoarthritis, rheumatoid arthritis, and ankylosing spondylitis. We will be using the recommended dosage of 100 mg twice a day over the course of 3 months. Celecoxib for TED is an off-label usage.

7. Study Statistics

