The primary study outcome is reduction of clinical activity of TED, as determined by both the CAS and VISA scores. We will use both scales because there is currently disagreement as to which scale serves as a better overall assessment tool. Secondary outcome measures will include reduction of specific aspects of TED, including proptosis, diplopia, and eyelid retraction. These elements are captured in part by the 2 scales but also will be evaluated separately. Change in quality of life will be measured by a validated questionnaire as another secondary outcome measure. Comparison of our primary outcomes between treatment and control groups will provide us with an indication of the relative efficacy of celecoxib treatment. Treatment safety also will be assessed, and adverse events recorded. A recent prospective study of intravenous corticosteroid dosing for TRO reported major adverse events in 10/159 (6.3%) of subjects and minor adverse events such as gastric distress, mild BP increase not requiring medication, and local skin reactions in about 25% of subjects. We anticipate a lesser incidence of minor or major adverse events based on the side effect profile of celecoxib in patients without co-morbidities placing them at higher risk (most TED patients are young and otherwise healthy). Occurrence of adverse events at a rate greater than what has been reported for intravenous corticosteroid (an accepted method of TED treatment) would suggest that risk of celecoxib treatment exceeds any benefit. Observation of adverse events in excess of this rate during the treatment phase would require review, and consideration of early study termination. The changes in either the CAS or VISA score will be compared between the celecoxib and observation groups to determine whether a trend or significant difference can be found.

8. Risks

The study procedures, apart from the proposed treatment, carry no risk beyond that of standard clinical care. Celecoxib has well-described risks especially in certain patient populations, who will be excluded from this study as noted. Below is an enumeration of risks copied from the package insert:

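### The only trial-level safety yardstick is a published intravenous-steroid rate; no adverse-event comparison with the randomised observation arm is planned, and safety ascertainment looks unequal between arms

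*Combined protocol and SAP*

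**What the plan says.** **Arms.** Section 4 (Study Procedures): "Study subjects will be randomly assigned to observation with no prescription treatment, or treatment with oral celecoxib 100 mg twice daily for 3 months". Section 5 gives the size: "Target 40 participants will be enrolled in this study". No allocation ratio is stated.

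**Yardstick.** The Outcomes bullet of Section 4 and Section 7 (Study Statistics) both cite a study of intravenous corticosteroid that "reported major adverse events in 10/159 (6.3%) of subjects", with minor events in about 25%. Both say that an adverse-event frequency "greater than what has been reported for intravenous corticosteroid (an accepted method of TED treatment) would suggest that risk of celecoxib treatment exceeds any benefit". Section 7 adds that exceeding the rate while patients are on treatment calls for review and for considering early termination.

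**Comparisons between arms.** Section 7 names the change in CAS or VISA score for comparison between celecoxib and observation. For safety, it and Section 4 say only that it will be assessed and events recorded. No comparison of event rates between arms is named.

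**Who is monitored.** One bullet of Section 4 opens "For those subjects randomized to the treatment group, baseline blood testing" and limits the repeat tests at 1 and 3 months to those taking celecoxib. The same bullet continues: "Monthly phone interviews also will be conducted by physician study team members to determine if other side effects, such as edema, may be occurring". It then lists the prompted questions (swelling, blood in the urine, skin discoloration, exercise tolerance) and ends with a caution about other NSAIDs while on celecoxib. No equivalent questioning or testing is described for observation. Both arms attend the same clinic visits at baseline and at 1, 3, 6 and 12 months.

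**The concern.** The yardstick sentence weighs risk against benefit, but the two sides have different references. The randomised benefit is the gain over observation. The risk is set against intravenous corticosteroid, which Section 1 (Abstract) itself describes as having significant morbidity. For a patient choosing between celecoxib and observation, the relevant harm is what celecoxib adds to the background rate, and the steroid figure does not supply that at any sample size.

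The observation arm could supply the background rate over the same months, but the plan as written does not collect it on equal terms. Two errors follow. A real excess over observation can sit below the steroid rate and raise no alarm. Conversely, symptoms that would have occurred anyway, once prompted for, count in full against celecoxib with no control rate to subtract.

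**Working it through.** **Inputs from the documents.** Total 40 (Section 5); benchmark 10/159 major and about 25% minor (Sections 4 and 7); the alarm is a rate above the benchmark.

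**Assumptions.** 1:1 allocation, so 20 on celecoxib; the benchmark applied separately to patients with major and with minor events (the plan does not say how it is applied); all true event rates and capture fractions below. The plan gives no expected rate for either arm.

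**1. The plan's own figure.** 10/159 = 0.0629, which matches 6.3%. The exact (Clopper-Pearson) 95% interval is 3.1% to 11.3%.

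**2. What trips the alarm with 20 treated.**
- Major: 1/20 = 5% is below 6.3% and 2/20 = 10% is above, so the alarm needs at least 2 patients.
- Minor: 5/20 = 25% is not above 25%, so the alarm needs at least 6 patients.

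**3. How often the alarm is silent.** For minor events the formula is P(X ≤ 5), with X binomial(20, p).

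| Assumed true minor rate on celecoxib | P(alarm silent) |
|---|---|
| 15% | 0.933 |
| 20% | 0.804 |
| 25% (equal to the benchmark) | 1 − 0.383 = 0.617 |

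At 20% on celecoxib against an assumed 5% on observation, the excess is 15 points and the alarm is silent in about 80% of trials. The 5% does not enter the calculation: the alarm gives the same answer whatever happens under observation. With 15 treated, the alarm needs 4 patients and is silent in 1 − 0.352 = 65% of trials at a true 20%. With 25 treated, it needs 7 and is silent in 1 − 0.220 = 78%. For major events at a true 5% with 20 treated, it is silent in 1 − 0.264 = 74%.

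**4. Effect of unequal questioning on an unplanned comparison.** Let the true rate be 20% in both arms, with full capture on celecoxib and a fraction c captured on observation. The spurious difference is 0.20 − 0.20c:
- c = 0.75: 5 points
- c = 0.50: 10 points
- c = 0.25: 15 points

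**5. Precision of a planned comparison.** With 20 per arm and rates of 20% and 5%, the 95% half-width of the risk difference is 1.96 × √(0.20×0.80/20 + 0.05×0.95/20) = 1.96 × √0.010375 = 0.20, or about 20 points. At 25% against 5% it is about 21 points. Power at two-sided 0.05 for 20% against 5% is 17% (Fisher's exact test) or 30% (normal approximation); 80% power would need about 76 per arm. The comparison supports an estimate with an interval, not a test.

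**The case against.** **The steroid benchmark is a legitimate question.** Section 4 also intends to set outcomes beside published steroid studies, and Section 8 (Risks) warns that observation may leave irreversible changes. Asking whether celecoxib is no more toxic than an accepted treatment is reasonable. This stands: the benchmark has a use, and it is the only numerical trigger for review in Section 7. A reader might infer that it is simply wrong and should be reduced to background; the documents do not support that.

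**The alarm is not a pass rule.** A reader might infer that a rate below the benchmark clears celecoxib. The plan says only what a higher rate would suggest. The 80% and 93% figures therefore show how often the alarm is silent, not how often celecoxib is declared safe. They also include small-sample chance, which is a separate matter from the choice of reference.

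**A comparison is still possible.** A reader might infer that the trial cannot show added harm at all. That is too strong. Both arms attend the same visits, and events are recorded without an arm limit. A crude comparison could be made, but it would be unplanned and unevenly ascertained. Section 4 also provides for action on individual patients and reporting to the IRB, but neither estimates added harm.

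**The limit on the telephone questions is inferred.** Those sentences name no arm, nor does the later safety-monitoring bullet where it mentions telephone surveillance. The opening of the bullet, the reference to other side effects and the NSAID caution favour the celecoxib-only reading. The laboratory restriction is explicit. The absence of a planned comparison holds on either reading.

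**Conclusion.** The point holds in this form. The sole trial-level safety yardstick is external, from a treatment neither arm is assigned. No adverse-event comparison with observation is planned. Active ascertainment is explicitly unequal for laboratory tests and apparently unequal for symptoms. The plan as written therefore yields no usable control rate for its risk-benefit statement, although the randomised arm that could provide one is already being seen.

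The size is illustrative only. With 20 treated and a true minor rate of 20%, the alarm is silent in about 80% of trials (65% with 15 treated, 78% with 25). Half capture under observation would create a spurious 10-point excess when the true rates are equal at 20%. These figures rest on assumed event rates, capture fractions and allocation. The efficacy analysis is not affected. The change should be made because it corrects the reference for the safety conclusion at little cost.

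**What to change.** In Section 4:
- Ask both arms the same symptom questions, in the same words, at the month 1 and month 3 visits that all subjects already attend.
- State explicitly which arm receives the monthly calls.

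In Section 7:
- Report major and minor adverse events by arm, with the risk difference and 95% CI, from these visit data.
- List events found by telephone or laboratory test in the celecoxib arm separately, so that they do not enter the comparison.
- Have the final risk-benefit statement report this difference alongside the steroid benchmark.
- Leave the existing benchmark trigger for review and possible early termination in place.

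**Cost.** A few added questions at existing visits and one table; no new visits. The interval will be wide, roughly plus or minus 20 points at an assumed 20 per arm, and should be presented as an estimate. Some reporting bias will remain, because no blinding is described and celecoxib subjects would still receive prompted calls between visits.

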- Outcomes: The primary study outcome is reduction of clinical activity of TED, as determined by both the CAS and VISA scores. We will use both scales because there is currently disagreement as to which scale serves as a better overall assessment tool. Secondary outcome measures will include reduction of specific aspects of TED, including proptosis, diplopia, and eyelid retraction, as well as a validated TED-specific quality of life survey. These elements are captured in part by the 2 scales but also will be evaluated separately. Comparison of our primary and secondary outcomes between the treatment and control groups and with published studies of steroid treatment for TED may provide us with an indication of the relative efficacy of celecoxib treatment and whether further study is warranted. Treatment safety also will be assessed, and adverse events recorded. A recent prospective study of intravenous corticosteroid dosing for TED reported major adverse events in 10/159 (6.3%) of subjects and minor adverse events such as gastric distress, mild BP increase not requiring medication, and local skin reactions in about 25% of subjects. We anticipate a lesser incidence of minor or major adverse events based on the side effect profile of celecoxib in patients without co-morbidities placing them at higher risk (most TED patients are young and otherwise healthy). Occurrence of adverse events at a rate

greater than what has been reported for intravenous corticosteroid (an accepted method of TED treatment) would suggest that risk of celecoxib treatment exceeds any benefit.

- Biospecimens will be collected in this study, to include urine for a pregnancy test for female patients of childbearing age to determine eligibility, as well as blood as noted above that will be drawn by the clinical lab.
- Study length: Subjects will be followed for 12 months.
- Safety monitoring: As noted, baseline blood testing and phone surveillance will be performed. If abnormal results are found during drug treatment, then subjects will be advised to stop the medication and will be examined by the PI or other MD investigator. Adverse events will be reported to the IRB per institutional policy.
- Subjects may be taken out of the study if:
 - Staying in the study would be harmful.
 - Treatment required is not allowed in the study.
 - Those that fail to follow instructions.
 - Subjects become pregnant.
 - The study is cancelled.

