- **Cardiovascular warning:** All prescription NSAIDs, like CELEBREX, ibuprofen, naproxen, and meloxicam have the same cardiovascular warning. They may all increase the chance of heart attack or stroke that can lead to death. This chance increases if you have heart disease or risk factors for it, such as high blood pressure or when NSAIDs are taken for long periods. Congestive heart failure and peripheral edema has also occurred in some patients has also been noted.
- CELEBREX should not be used right before or after certain heart surgeries.
- Stomach and intestine risk: All prescription NSAIDs have the same warning for serious stomach and intestine problems: They may cause ulcers and bleeding, which can occur without warning and may cause death.
- **Renal warning:** Long term use of NSAIDs, like CELEBREX, have resulted in renal papillary necrosis. Patients at risk are those with impaired renal function, heart failure, liver dysfunction, those taking diuretics, ACE inhibitors, and angiotension II inhibitors.

Date: January 21, 2017 Principal Investigator: [name] Application Number: IRB00094787

• Serious skin and allergic reactions can occur with CELEBREX. CELEBREX shold not be taken if one has had an asthma attack, hives, or other allergies to aspirin, other NSAIDs, or certain drugs called sulfonamides.

Risks of corticosteroid treatment are noted in section 7 with at least 25% of patients experiencing a minor or major adverse event. Orbital radiotherapy carries theoretic risk of ocular radiation toxicity (cataract formation, radiation retinopathy or optic neuropathy) and second malignancy occurrence, but the actual rate of such events is not known. Untreated, some patients with TED may have spontaneous improvement while others will progress to more severe manifestations. Increased disease activity at presentation is a predictor for progression, and we thus are including only subjects with clinical activity that may put them at risk for such changes. Treatment is effective only during the active phase of TED, and observation may result in irreversible proptosis or strabismus requiring subsequent surgery.

9. Benefits

The major benefit of the study is anticipated to be reduction of TED severity as measured by clinical activity assessment.

10. Payment and Remuneration

Subjects will not be compensated for participation.

11. Costs

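### A raw adverse-event excess over the published steroid rate in about 20 treated patients cannot by itself support the reading that risk exceeds benefit

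*Combined protocol and SAP*

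**What the plan says.** Section 7 (Study Statistics) describes a published study of intravenous corticosteroid that "reported major adverse events in 10/159 (6.3%) of subjects and minor adverse events" in about 25% of subjects. It then states an expectation: "We anticipate a lesser incidence of minor or major adverse events based on the side effect profile of celecoxib".

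Next comes the sentence at issue, which appears in both Section 4 (Outcomes) and Section 7. It sets the bar at a rate "greater than what has been reported for intravenous corticosteroid" and ends "an accepted method of TED treatment) would suggest that risk of celecoxib treatment exceeds any benefit". Section 7 alone adds the consequence: "Observation of adverse events in excess of this rate during the treatment phase would require review, and consideration of early study termination".

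Section 8 (Risks) restates the steroid figure as a combined one: "at least 25% of patients experiencing a minor or major adverse event".

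On efficacy, Section 7 uses the randomised control arm: "Comparison of our primary outcomes between treatment and control groups will provide us with an indication of the relative efficacy of celecoxib treatment". Neither section plans the same for adverse events. Section 5 gives a target of 40 participants. Section 4 describes random assignment to two arms without stating an allocation ratio.

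**The concern.** Read as written, any observed rate above the published one points to risk exceeding benefit. Three features make that inference weak.

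- **Chance.** In about 20 patients, one or two events more than expected put the raw rate above the benchmark. No interval is planned for the trial rate, and the benchmark rests on only 10 events.
- **Which benchmark.** The rate meant could be 6.3% (major), about 25% (minor), or at least 25% (minor or major, as in Section 8). With 20 treated, this moves the smallest exceeding count from two to five or six.
- **What is compared.** The sentence sets celecoxib risk against steroid risk, yet concludes about celecoxib's benefit without using any efficacy result. The concurrent randomised arm is not used for safety.

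At stake is the safety conclusion. A drug no more harmful than the accepted comparator could be described as having risk above its benefit on the strength of one extra event. The opposite error is also possible: a low count could be taken as showing celecoxib to be safer than steroid.

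**Working it through.** **Inputs.** Total 40 (Section 5). Allocation ratio not stated; 1:1 assumed, so n = 20 treated, with 18-22 as the range. Benchmarks 10/159 and about 25% (Section 7). A single look at the end is assumed, and the benchmark is treated as fixed.

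**The plan's own figure.** 10/159 = 0.0629, which matches the stated 6.3%. The expected count in 20 patients is 20 × 0.0629 = 1.26.

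**Major events.** One event is 1/20 = 5.0%, below the benchmark; two are 10.0%, above it. With X ~ Binomial(20, p):

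P(X ≥ 2) = 1 − (1−p)^20 − 20p(1−p)^19

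- At p = 0.0629: 1 − 0.273 − 0.366 = 0.361.
- At p = 0.03: 1 − 0.544 − 0.336 = 0.120.

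For n = 18, 19, 20, 21, 22 at p = 0.0629 the chance of an excess is 0.314, 0.338, 0.361, 0.384, 0.407.

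**Minor events.** The published figure is only approximate, and 5/20 is exactly 25%, so the threshold at n = 20 depends on which side of 25% the true published figure lies. As an illustration, assume it came from the same 159 subjects: 39/159 = 24.5% and 40/159 = 25.2%.

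| Benchmark (true rate equal to it) | Count needed at n = 20 | Chance of excess at n = 20 | Range, n = 18-22 |
|---|---|---|---|
| 39/159 | 5 | 0.566 | 0.41-0.57 |
| exactly 25% | 6 | 0.383 | 0.38-0.53 |
| 40/159 | 6 | 0.389 | 0.39-0.54 |

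The chance is therefore about 38-57%. At a true minor rate of 15% and n = 20, it is P(X ≥ 6) = 0.067 if six events are needed and P(X ≥ 5) = 0.170 if five are.

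**What such counts can show** (Clopper-Pearson 95% intervals):

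| Count | Interval |
|---|---|
| 2/20 | 1.2-31.7% |
| 6/20 | 11.9-54.3% |
| 0/20 | 0-16.8% |
| 10/159 (benchmark) | 3.1-11.3% |

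Fisher's exact test of 2/20 against 10/159 gives p = 0.63. A large excess is different: 5/20 has an interval of 8.7-49.1% and p = 0.015 against 10/159, and 10/20 has an interval of 27.2-72.8%, above 25%.

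**Ascertainment.** Section 4 schedules the clinical exams for all patients, but the blood tests begin "For those subjects randomized to the treatment group, baseline blood testing for blood counts, renal and hepatic function" and are repeated only for those receiving celecoxib. It does not say clearly whether the monthly calls go to controls. A between-arm difference is like for like only for events looked for in both arms.

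**The case against.** The strongest reply is that the sentence is hedged. It says an excess would suggest something, and the only stated action is a review with early termination to be considered. A review trigger ought to be sensitive, and a 36% chance of an unnecessary review is a tolerable price. Sections 4 and 7 share nearly the same paragraph and should be read together. All of this stands as a defence of the trigger. It does not rescue the sentence as an interpretation: Section 4 carries it with no trigger attached, as a reading of the safety result.

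Second, equal rates are not what the plan expects, and the exclusions in Section 5 remove renal, hepatic and cardiac risk. This also stands, and it is why the 12%, 7% and 17% figures belong beside the 36%. A lower expected rate makes a chance excess rarer; it does not make the inference sound when one occurs.

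Third, this is a small trial meant partly to indicate whether further study is warranted, and the between-arm comparison will be imprecise. True, but that argues for showing the imprecision.

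Two stronger readings are tempting. A reader might infer that the trial has about a one-in-three chance of being stopped wrongly; the documents prescribe review and consideration, not stopping. A reader might also infer that the plan means to demonstrate fewer events than with steroid and cannot. The lower incidence is stated as an expectation, not as a planned test. The 16.8% upper limit for 0/20 is a caution against over-reading a low count, not a failed objective.

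**Conclusion.** The point holds as a minor one about interpretation. With about 20 treated patients, a raw rate above the published steroid rate cannot by itself support a statement that risk exceeds benefit. At true rates equal to the benchmark, an excess appears by chance 36% of the time for major events (31-41% for 18-22 treated) and about 38-57% of the time for minor events. These are chances of any excess, not only a small one. At lower true rates the chance is clearly smaller.

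The figures assume 1:1 allocation, a single look and a fixed benchmark; the minor-event range also assumes that the published figure lies close to 25% on one side or the other. The conclusion does not depend on n being exactly 20. It does not extend to a large excess, such as 5/20 major or 10/20 minor, whose exact interval lies above the published figure.

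**What to change.** Leave the review trigger and individual medical review as they are. In Sections 4 and 7:

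1. Compare major events with 6.3% and minor events with about 25%, separately.
2. Report each celecoxib rate, and 10/159, with an exact 95% interval.
3. Report the celecoxib-minus-observation difference with an exact interval for events ascertained in both arms, for example at the scheduled exams. Report findings from the celecoxib-only blood tests, and from the calls if controls do not receive them, for that arm alone.
4. Replace the sentence on risk exceeding benefit with wording such as: *A raw excess prompts review. It is interpreted with its exact interval, the difference from the observation arm and the efficacy result. Neither an excess nor a low count whose interval includes the published figure shows that celecoxib is worse or safer than intravenous corticosteroid.*

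The interval should not become a hurdle for raising a safety concern. Requiring the lower 95% limit to pass 6.3% would need 5/20, and a true doubling to 12.6% would then be missed with probability P(X ≤ 4) = 0.90 at n = 20 (0.82-0.92 for 18-22).

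**Cost.** A few lines of text, with no added visits, tests or calls. The safety conclusion becomes more cautious. The between-arm interval will be wide: 2/20 against 0/20 is +10 points, with an exact interval of about −8 to +32. That difference also omits laboratory abnormalities tested in one arm only. Intervals address chance alone; the documents do not give the published study's full event definitions or exposure, so the external comparison stays limited.

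### Section 7's only trial-level safety trigger is an event rate: on its strictest reading, a lone grave event does not meet it once 16 or more subjects have been treated

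*Combined protocol and SAP*

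**What the plan says.** Section 7 cites a prospective study of intravenous corticosteroid dosing with major adverse events in 10 of 159 subjects (6.3%) and minor ones in about 25%. It treats a higher rate on celecoxib as a sign that risk outweighs benefit, and then gives the trial-level rule: "Observation of adverse events in excess of this rate during the treatment phase would require review, and consideration of early study termination". It does not say whether the rate meant is the major, the minor or a combined one, which subjects form the denominator, or when the rate is computed. Section 8 refers back to the benchmark as "with at least 25% of patients experiencing a minor or major adverse event", which suggests that a pooled reading is possible.

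The remaining safety provisions, all in Section 4, act on single subjects or on reporting. For the monthly phone interviews, "Positive responses will trigger an unscheduled visit with the PI or co-investigator MD". For abnormal results during treatment, "subjects will be advised to stop the medication and will be examined by the PI or other MD investigator". The list of reasons for taking a subject out includes cancellation of the study, but gives no criterion for cancelling it. On reporting, "Adverse events will be reported to the IRB per institutional policy".

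Section 8, reproducing the package insert, says of prescription NSAIDs as a class: "They may all increase the chance of heart attack or stroke that can lead to death". On the stomach and intestine it says: "They may cause ulcers and bleeding, which can occur without warning and may cause death". Neither hazard is tied to a trial-level action. Section 5 gives the size: "Target 40 participants will be enrolled in this study".

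**The concern.** A rate threshold is a reasonable guard against an excess of ordinary adverse events. It suits rare, grave events poorly in a trial this small, because one event is a large percentage early on and a small one later. Whether a fatal infarction meets the rule then depends on how many subjects have been treated when it is counted, and not on what happened.

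This matters because the protocol itself names death, heart attack, stroke and GI bleeding as hazards of the drug class, the use is off-label (Section 6), and the control arm receives no prescription treatment. One such event in a celecoxib subject is a reason to ask whether the trial should go on, even if the running percentage stays below a benchmark taken from a different drug.

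**Working it through.** **Inputs.** Benchmark for major events: 10/159 (Section 7). Benchmark for minor events: about 25% (Section 7). Total enrolment: 40 (Section 5). The allocation ratio is not stated; 1:1, so 20 on celecoxib, is an assumption. The documents give no rate for death, infarction, stroke or serious GI bleeding on celecoxib, so a range of 0.1% to 1% per subject over the treatment phase is assumed.

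**Step 1: the plan's own figure.** 10/159 = 0.06289, which rounds to the printed 6.3%.

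**Step 2: one event, strictest reading.** The rule is met if k/n is greater than 10/159, where k counts major events and n counts celecoxib recipients. With k = 1:

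| n treated | 1/n | Above 6.29%? |
|---|---|---|
| 14 | 7.14% | yes |
| 15 | 6.67% | yes |
| 16 | 6.25% | no |
| 20 | 5.00% | no |

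The cut-off is the same with the rounded 6.3%. At n = 20 a second major event of any kind gives 2/20 = 10% and the rule is met.

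**Step 3: other readings.**
- All enrolled subjects as denominator: at 40 enrolled, 1/40 = 2.5% and 2/40 = 5.0% do not meet the rule; 3/40 = 7.5% does.
- 25% as threshold: one event alone meets it only for n of 3 or fewer (1/3 = 33.3%; 1/4 = 25.0% is not in excess). At n = 20, six events are needed, since 5/20 is exactly 25%. If minor events count too, they mostly decide whether the rule is met.

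Each of these makes a lone grave event less likely to meet the rule than in Step 2.

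**Step 4: how often the gap could matter.** With event probability p per subject and 20 treated:
- P(at least one grave event) = 1 − (1 − p)^20 = 0.020 at p = 0.1% and 0.18 at p = 1%.
- P(exactly one) = 20p(1 − p)^19 = 0.0196 at p = 0.1% and 0.165 at p = 1%.

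If the rate were checked once, at n = 20, the second line is an upper bound on the chance that a grave event occurs and the strictest rule is not met. It is only a bound because another major event would trip the rule. If other major events occur in a fraction q of subjects, the chance of none among the other 19 is (1 − q)^19: 0.83 at an assumed 1%, 0.56 at 3%, 0.29 at 6.3%. The bound at p = 1% then falls to about 0.165 × 0.83 = 0.137, or 0.165 × 0.29 = 0.048.

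With a running count the chance is lower, but it cannot be calculated. Treatment lasts 3 months and subjects overlap, so an event in the tenth celecoxib subject might be counted when 12 have started (rule met) or 16 (not met). The documents give no accrual rate.

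**Step 5: cost of a single-event trigger.** Expected treatment-phase events among 20 treated: 20 × 0.001 = 0.02 to 20 × 0.01 = 0.2.

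**The case against.** The strongest case against is that the gap may have no practical effect. Adverse events go to the IRB under institutional policy, and that policy may already prompt a review after one death or infarction. Nothing in the protocol bars an ad hoc review. The events should also be rare: Section 5 excludes heart failure, valvular and coronary disease, antihypertensive treatment other than beta-blockers, and earlier NSAID reactions such as GI bleeding. The dose is 100 mg twice daily for 3 months, with monthly physician calls and laboratory tests at 1 and 3 months.

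Most of this stands. It means that the gain over IRB reporting cannot be quantified, since the policy is not in the documents. It does not supply the missing trigger: the protocol sets its own condition for reviewing the trial, and that condition does not call for review of a lone event late in accrual.

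A second objection is that severity is not absent from the rule. This also stands. A reader might infer that the trigger is blind to what the event is, but the benchmark separates major from minor events, and the cut-off between 15 and 16 exists only if the rule is restricted to major ones. What is missing is narrower: a single-event trigger within the major class.

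**Conclusion.** The point holds as a gap in the stated rule. With major events as numerator, celecoxib recipients as denominator and no other major event, one death, infarction, stroke or serious GI bleed meets the rule among 15 or fewer treated and not among 16 or more. The other readings of the rate or denominator make it harder to meet. That 20 subjects will be treated rests on assumed 1:1 allocation; the cut-off itself does not.

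Two stronger inferences are not supported. One is that a lone event at full enrolment always escapes the rule, or that a fixed share of lone events does, for instance 5 of 20 by enrolment position. The first ignores other major events; the second treats enrolment position as the number treated when the event is counted. The probabilities of about 0.020 to 0.165 for a single look at 20 treated are upper bounds under an assumed event rate. The other inference is that such an event would go unexamined, which the IRB reporting provision contradicts.

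This is a change worth making because the outcome may be fatal and the remedy is cheap, not because the event is likely.

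**What to change.** Keep the rate rule and add one sentence to Section 7:

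*Any single death, myocardial infarction, stroke, serious GI bleed (hospitalisation or transfusion) or other life-threatening event in a celecoxib subject during the treatment phase, or later if judged possibly related to celecoxib, triggers the same review and consideration of early termination, whatever the running rate.*

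The time limit keeps unrelated events in the 9 months after treatment (12 months of follow-up less 3 on drug) from prompting a review, and the severity qualifier leaves out trivial bleeds. The sentence works whichever rate, denominator or look time the sponsor intended. It requires review, not stopping, and needs no new committee and no change to sample size or analysis.

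The cost is an occasional review prompted by an unrelated event: about 0.02 to 0.2 expected over 20 treated subjects under the assumed treatment-phase rate of 0.1% to 1%. Later events judged possibly related would add to that and are not in the figure.
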